- Imaging analysis must be using the same technique during the study, e.g. it's not allowed to use CT scan at baseline then change to MRI during the study. Tumor response will be assessed, within 1 week prior to Day 1 of Cycles 3, 5, and 7, and every third cycle thereafter. Subjects who discontinue treatment will undergo EOT visit procedures.

Table 4

Schedule of Pharmacokinetic, Electrocardiogram Assessments and Food Guidance during Part 2A M8891 Combined with Cabozantinib, mRCC, Dose Escalation

Treatment Day	Time h (\pm min) ^{a,b}	ECG ^c	PK M8891	PK Cabozantinib
Day -1, C1	Pre-dose (-60 min)	X	X ^d	
	1 (\pm 5)		X ^d	
	2 (\pm 10)	X	X ^d	
	3 (\pm 15)		X ^d	
	4 (\pm 15)		X ^d	
	6 (\pm 15)	X	X ^d	
	8 (\pm 15)		X ^d	
D1 C1	Pre-dose (-60 min)	X	X	X
	1 (\pm 5)		X	
	2 (\pm 10)	X	X	X
	3 (\pm 15)		X	
	4 (\pm 15)		X	
	6 (\pm 15)	X	X	X
D8 C1	Pre-dose (-60 min)	X	X	X
	2 (\pm 5)	X	X	X
D15 C1	Pre-dose (-60 min)	X	X	X
	1 (\pm 5)		X	
	2 (\pm 10)	X	X	X
	3 (\pm 15)		X	
	4 (\pm 15)		X	
	6 (\pm 15)	X	X	X
D1C2	Pre-dose (-60 min)	X	X	X
	2 (\pm 10)	X	X	X
D1C3-5	Pre-dose (-60 min)	X		
	1 (\pm 5)	X		
D1C7 (and Day 1 of every third cycle)	Pre-dose (-60 min)	X		
	1 (\pm 5)	X		

C: Cycle; D: Day; ECG: Electrocardiogram; eCRF: Electronic case report form; mRCC: Metastatic renal cell carcinoma; PK: Pharmacokinetics.

a. At visits where assessment time points (ECG and PK) coincide with each other

- 1) Perform vital signs assessments at first
- 2) ECG assessments slightly before the specific collection time point
- 3) PK assessments at scheduled collection time point.

b. Actual collection times should be documented in the eCRF.

- c. Standard triplicate (within 2 min) 12-lead ECG will be obtained after the subject has been rested in semi-recumbent position for at least 5 min at the indicated times. ECGs will be also performed during the End of Treatment and Safety Follow-up Visit (30 ± 7 days). Triplicate ECGs will be read locally. The calculated QTcF interval average of the three 12-lead ECGs must be ≤ 450 ms for males and ≤ 470 ms for females for eligibility. Subjects, in which the calculated QTcF interval average increases to > 500 ms or > 60 ms change over baseline during treatment, must interrupt study treatment until further clinical evaluations (See Section 7.4.5).

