- d. All subjects in Part 2A will receive on Day -1, Cycle 1 a single dose of M8891 with a high calorie, high-fat breakfast. PK data collected at the indicated times will be compared with those obtained at the same dose-levels in Part 1 where subjects have received M8891 under fasted conditions.

Table 5

Schedule of Pharmacokinetic and Electrocardiogram Assessments during Part 2B M8891 Combined with Cabozantinib, mRCC, Expansion Cohort

Treatment Day	Time h (\pm min) ^{a,b}	ECG ^c	PK M8891	PK Cabozantinib
D1 C1	Pre-dose (-60 min)	X	X	X
	2 (\pm 10)	X	X	
	6 (\pm 15)	X	X	X
D8 C1	Pre-dose (-60 min)	X	X	X
	2 (\pm 5)	X	X	X
D15 C1	Pre-dose (-60 min)	X	X	X
	2 (\pm 10)	X	X	
	6 (\pm 15)	X	X	X
D1C2	Pre-dose (-60 min)	X		
	2 (\pm 5)	X		
D1C3-5	Pre-dose (-60 min)	X		
	1 (\pm 5)	X		
D1C7 (and Day 1 of every third cycle)	Pre-dose (-60 min)	X		
	1 (\pm 5)	X		

C: Cycle; D: Day; ECG: Electrocardiogram; eCRF: Electronic case report form; mRCC: Metastatic renal cell carcinoma; PK: Pharmacokinetics.

- a. At visits where assessment time points (ECG, and PK) coincide with each other
 - 1) Perform vital signs assessments at first
 - 2) ECG assessments slightly before the specific collection time point
 - 3) PK assessments at scheduled collection time point
- b. Actual collection times should be documented in the eCRF.
- c. Standard triplicate (within 2 min) 12-lead ECG will be obtained after the subject has been rested in semi-recumbent position for at least 5 min at the indicated times. ECGs will be also performed during the End of Treatment and Safety Follow-up Visit (30 \pm 7 days). Triplicate ECGs will be read locally. The calculated QTcF interval average of the three 12-lead ECGs must be \leq 450 ms for males and \leq 470 ms for females for eligibility. Subjects, in which the calculated QTcF interval average increases to $>$ 500 ms or $>$ 60 ms change over baseline during treatment, must interrupt study treatment until further clinical evaluations (See Section 7.4.5).

2 Sponsor, Investigators and Trial Administrative Structure

This clinical trial will be sponsored by EMD Serono Research & Development Institute, Inc., Billerica, MA, USA.

The Sponsor's legal representative in the EU is Merck KGaA, [name].

The Part 1 of the trial will be conducted at approximately 5 sites in USA. The Part 2 of the trial will be conducted at approximately 7 sites in USA.

The Coordinating Investigator **PPD**

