Corrected QTcF interval Prolongation	
If at any time on study the average QTcF interval from the 3 ECGs is > 500 ms, the following actions should be taken:
 
 • Withhold study treatment • Immediately notify the Sponsor • Hospitalize symptomatic subjects (e.g., with palpitations, dizziness, syncope, orthostatic hypotension, a significant ventricular arrhythmia on ECG) for a thorough cardiology evaluation and management • Consider cardiology consultation for asymptomatic subjects for evaluation and management • Check electrolytes, especially magnesium, calcium, and potassium; correct abnormalities as clinically indicated • Check concomitant medications for any medication that may have contributed to QT prolongation, and if possible, discontinue these medications (refer to http://www.qtdrugs.org) • Repeat ECG triplicates hourly until the average QTcF interval is ≤ 500 ms • Subjects with QTcF interval prolongation and symptoms must be monitored closely until the QTcF interval prolongation and symptoms have resolved. 
Study treatment may be restarted at a reduced dose level if ALL the following conditions are met:
 
 • Symptoms are determined to be unrelated to the QT interval prolongation • The QTcF interval value returns to ≤ 500 ms • Study treatment has been interrupted through a minimum of 1 week following the return of the QTcF interval to ≤ 500 ms • QT prolongation can be unequivocally associated with an event other than study treatment administration and is treatable/has been resolved • Sponsor has reviewed all available information and has agreed to the continuation of study treatment 
Following reinitiation of study treatment, ECGs must be repeated weekly for 2 weeks, then every 2 weeks for 1 month, then according to the protocol-defined time points.
 
Study treatment must be permanently discontinued if either of the following applies:
 
 • Cardiac evaluation confirms that symptoms are the consequence of QT interval prolongation • Recurrence of QTcF interval prolongation after reinitiation of study treatment at a reduced dose

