During the scheduled safety visits, subjects, in whom the calculated QTcF interval average increases to $>$ 500 ms or $>$ 60 ms change over baseline during treatment with M8891 combined with cabozantinib, must interrupt study treatment until further clinical evaluation. ECGs should be repeated if QTcF interval is outside the range until resolution (Table 12, Section 6.5.5). To assess the safety and tolerability of the study intervention, an ECG can be repeated at the Investigator's discretion at unscheduled visits. Start and end of resting time and ECG time will be recorded in the eCRF.

Abnormalities in the ECG that lead to a change in subject management (e.g., dose reduced or withheld, treatment discontinued, requirement for additional medication or monitoring as described in Table 12, Section 6.5.5) or result in clinical signs and symptoms are considered clinically significant for the purposes of this study and will be deemed adverse events. If values meet criteria defining them as serious, they must be reported as SAEs.

7.5

Pharmacokinetics

7.5.1

Part 1, M8891 Single Agent, Solid Tumors

For the PK analysis, the plasma level of M8891 will be analyzed by the analytical laboratory selected under responsibility of the Sponsor, using an appropriate validated bioanalytical method. Urine level of M8891 will be analyzed using an appropriate qualified method.

Full details of the bioanalytical method used will be described in a separate bioanalytical report. Plasma concentrations of M8891 and its metabolites will be analyzed as indicated in Table 1.

At each time point, 3 mL (2 aliquots of 1.5 mL) blood will be collected. The exact blood volume will be indicated in the Laboratory Manual. For all clinical and research studies, the total blood volume (mL) drawn in a 30-day period will never exceed the 280 mL.

Actual date and time of M8891 administration and PK actual sampling date and time will be recorded in the eCRF.

The PK sampling (and corresponding CCI sampling) schedule may be modified based upon emerging PK information collected during the study with the provision that the overall amount of blood to be collected for PK sampling is not increased.

List of PK parameters:

- C_{max} : Observed maximum plasma concentration
- t_{max} : Time to reach maximum observed plasma concentration
- $AUC_{0-\infty}$: Area under the concentration-time curve from time zero extrapolated to infinity, based on the predicted value for the concentration at t_{last}

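### Part 2: after a hold for QTcF above 500 ms, the restart value and 1-week clock in Table 12 leave out the protocol's own limit of 60 ms over baseline

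*Protocol*

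**What the plan says.** **When to interrupt.** Table 4 footnote c (Part 2A) applies to subjects whose "calculated QTcF interval average increases to > 500 ms or > 60 ms change over baseline during treatment, must interrupt study treatment". Table 5 footnote c (Part 2B) has the same rule. Section 7.4.5.2 repeats it in the body text: "60 ms change over baseline during treatment with M8891 combined with cabozantinib, must interrupt study treatment until further clinical evaluation". The trigger has two limbs, an absolute value and a change from baseline. The hold lasts until clinical evaluation, with no numerical end.

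**Where resolution is defined.** Section 7.4.5.2 continues: "ECGs should be repeated if QTcF interval is outside the range until resolution (Table 12, Section 6.5.5".

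**What Table 12 says.** The QTcF row in Section 6.5.5 opens at a mean QTcF above 500 ms. It then gives three lines with a QTcF value:

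- Repeat ECGs: "Repeat ECG triplicates hourly until the average QTcF interval is ≤ 500 ms".
- Restart value: "The QTcF interval value returns to ≤ 500 ms".
- Clock: "Study treatment has been interrupted through a minimum of 1 week following the return of the QTcF interval to ≤ 500 ms".

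The restart rule is joint: "Study treatment may be restarted at a reduced dose level if ALL the following conditions are met". The remaining conditions are that symptoms are judged unrelated to QT prolongation, that the prolongation has an unequivocal cause other than study treatment which is treatable or resolved, and that the Sponsor has reviewed the case and agrees. After restart, ECGs are weekly for two weeks and then less frequent.

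**The concern.** The stopping rule looks at two quantities and the restart rule looks at one. After a hold for QTcF above 500 ms, Table 12 can count its QTcF condition as met, and can start the 1-week clock, at a value that the protocol elsewhere treats as reason to stop the drug. If treatment resumed with QTcF unchanged, the next on-treatment ECG would call for another interruption.

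At stake is consistent handling of a cardiac safety rule across about 7 sites that read their own ECGs. A site working from Table 12 and a site working from 7.4.5.2 could judge recovery differently on the same tracing. No efficacy endpoint or planned analysis depends on this.

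**Working it through.** The plan gives no figure to reproduce. The check compares thresholds.

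**Inputs**

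- Interruption: QTcF > 500 ms, or > 60 ms over baseline (Table 4 and Table 5 footnote c; 7.4.5.2).
- Table 12 restart value and clock: QTcF ≤ 500 ms.
- Eligible QTcF: up to 450 ms in men and 470 ms in women (Table 4 and Table 5 footnote c; 7.4.5.2).

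**Formula.** Let b be baseline QTcF. The interruption threshold is min(500, b + 60). The Table 12 threshold is 500. They differ when b + 60 < 500, that is, b < 440 ms. The gap is the interval (b + 60, 500], of width 440 − b.

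| Baseline (ms) | Interrupt above (ms) | Table 12 value (ms) | Gap (ms) |
|---|---|---|---|
| 380 | 440 | 500 | 60 |
| 400 | 460 | 500 | 40 |
| 410 | 470 | 500 | 30 |
| 420 | 480 | 500 | 20 |
| 430 | 490 | 500 | 10 |
| 440 or more | 500 | 500 | 0 |

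Within the eligible range, only baselines from 440 ms up are free of the gap: the top 450 − 440 = 10 ms for men and 470 − 440 = 30 ms for women.

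**Example.** Baseline is 410 ms and QTcF rises to 505 ms, so both limbs are exceeded (505 > 500; 505 − 410 = 95 > 60). Off drug it falls to 495 ms. Table 12's QTcF condition is met and the clock starts. The change from baseline is 495 − 410 = 85 ms, and 495 is 25 ms above the interruption threshold of 470.

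**After the fix.** With ≤ 60 ms over baseline added, the restart threshold becomes min(500, b + 60), the same as the interruption threshold, and the gap is empty at every baseline.

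**Side effect on Part 2A DLTs.** Section 5.1.3.3 counts an interruption of more than 7 days, or of more than 30% of the Cycle 1 dose, due to AEs not related to underlying disease or concomitant medication. Cycle 1 plans 21 cabozantinib doses and 22 M8891 doses (Day −1 plus 21).

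- Hold starting before the Day 15 dose: the existing 1-week minimum already costs at least 7/21 = 33.3% and 7/22 = 31.8%, both above 30%. The fix does not alter that.
- Hold starting after the Day 15 dose: at most Days 16 to 21 are lost in Cycle 1, 6/21 = 28.6% and 6/22 = 27.3%, with or without the fix. A longer hold could then matter only under the 7-day limb, if days in Cycle 2 are counted.

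**Why the action trigger should stay at > 500 ms.** A rise from 375 to 436 ms is +61 ms. Putting it under Table 12 would impose the 1-week minimum and the same 7/21 = 33.3% loss. Without that minimum, a 4-day hold costs 4/21 = 19.0%, which keeps the subject above the 80% dose needed for DLT evaluability. A 6-day hold costs 28.6%, still under 30%.

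**The case against.** The strongest objection is that the two rules are sequential. Section 7.4.5.2 starts a hold and Table 12 governs restart after a value above 500 ms. The hold runs only until clinical evaluation, and nothing says it must last until QTcF is within 60 ms of baseline. This stands. A reader might infer that at 495 ms on a baseline of 410 the protocol both requires a hold and permits restart. The documents do not support that: the subject is already off drug, and 495 ms would call for a new interruption only once treatment had resumed.

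Second, meeting the QTcF value and the clock does not permit restart. All conditions must hold, restart is at a reduced dose, and ECGs follow weekly. This also stands, and it limits the risk. But none of the other conditions sets a limit on change from baseline, and a cause that is merely treatable satisfies the cause condition.

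Third, the ≤ 500 ms line on repeat ECGs can be read as ending the hourly frequency, not ECG monitoring altogether. Section 7.4.5.2 separately asks for repeats until resolution. That reading is fair, so the line is not counted here as a mismatch.

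Fourth, a reader might infer that a subject held only for > 60 ms meets the Table 12 values from the outset. The wording does not support this. The row opens at > 500 ms, and its restart value and clock speak of a return to ≤ 500 ms. Such a subject is covered by 7.4.5.2: interruption, clinical evaluation and repeat ECGs.

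Finally, Section 5.1.3.5.3 has a general recovery rule (Grade ≤ 1 or baseline). The Table 12 QTcF row does not cite it, and no order of priority is stated, so it does not settle the matter.

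**Conclusion.** The point holds for Part 2 subjects held for QTcF > 500 ms whose baseline is below 440 ms. For them, Table 12's restart value and 1-week clock can both be satisfied above the protocol's own interruption threshold, by up to 440 minus baseline. The threshold comparison is exact and rests on the stated limits alone.

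How often this would happen cannot be estimated. The documents give no baseline QTcF distribution, so the tabulated baselines are illustrative. The path is narrow: a rise above 500 ms (more than 90 ms from a baseline of 410), a plateau inside the gap, and then every other restart condition met. Part 2 plans at most 15 + 40 = 55 subjects, and Section 3.3.1 reports no preclinical or preliminary clinical evidence that M8891 prolongs QTcF. This is a safety rule that should be corrected because it is inconsistent and cheap to align. It is not evidence that the plan would allow unsafe restarts in practice.

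**What to change.** 1. In the Table 12 QTcF row, add ≤ 60 ms over baseline to the QTcF restart condition and to the 1-week clock.
2. Keep the hourly-triplicate endpoint at ≤ 500 ms. State that repeat ECGs then continue at a lower frequency until QTcF is inside both limits.
3. In Section 7.4.5.2, state that resolution means mean QTcF ≤ 500 ms and ≤ 60 ms over baseline, with clinical evaluation still deciding on restart.
4. Do not add > 60 ms to the Table 12 action trigger. That would put small rises under the full list for > 500 ms and could create interruption DLTs. Leave 5.5.1, 5.1.3.5.3 and the other restart conditions as they are.

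The cost is a few lines of wording. A few subjects held for > 500 ms would stay off drug somewhat longer and have some extra ECGs. Any effect on Part 2A Cycle 1 DLTs is small. It arises only where the interruption is not attributed to underlying disease or concomitant medication, whereas Table 12 allows restart only when the prolongation has a cause other than study treatment. The sentence in 7.4.5.2 adds no minimum hold.

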3.2 Background

The discovery of fumagillin with potent anti-angiogenic and anti-proliferative activities promoted the development of MetAP2 antagonists as a novel class of anticancer agents. MetAP2 plays an important role in the development of different types of cancer. MetAP2 inhibition induces cytostasis by cell cycle arrest at the G1 phase selectively in endothelial cells and in a subset of tumor cells. MetAP2 inhibitors block neo-angiogenesis both in vitro and in vivo and show potent antitumor efficacy in a variety of tumor types in murine models.

In clinical trials fumagillin proved unsuitable as an anticancer agent due to its pronounced neurotoxicity. The reversible MetAP2 inhibitor M8891 is not chemically related to fumagillin and has not shown signs of neurotoxicity in toxicology studies. In comparison to irreversible MetAP2 inhibitors it has the promise of an improved safety and tolerability profile, which is the prerequisite for administration over extended periods.

RCC represents a heterogeneous group of cancers that arise from the kidney. The most common histological variant of RCC is clear cell RCC, which comprises about 70% of RCC and has the highest metastatic potential (Moch 2016). The genetic basis of clear cell RCC is via a biallelic inactivation of the VHL tumor suppressor gene (present in 70% of clear cell cancers) located on the short arm of chromosome 3 (3p25.3), which encodes for the degradation of HIF α (Kim 2004).

Medical treatment for mRCC has expanded considerably from a nonspecific immune approach to targeted therapies against VEGFR and mammalian target of rapamycin (mTOR). Today the salvage approach has evolved, to include immune checkpoint blockade (ICB) targeting programmed death-1 (PD-1) and programmed death-ligand 1 (PD-L1) (Salgia 2019). VEGFR TKIs alone, ICB, or VEGFR TKIs combined with ICB are preferred options for first-line treatment of mRCC. Cabozantinib, nivolumab, and axitinib are preferred subsequent therapy options. Given that cabozantinib appears to be active following earlier ICB and TKI regimens (as monotherapy or as combinations) (Barata 2018; Powles 2018.) and the MoA of MetAP2 inhibition is independent of the ICB MoA, a combination that synergizes with cabozantinib would still be expected to show efficacy.

3.3

Benefit/Risk Assessment

Based on the nonclinical data on M8891 showing evidence of tumor stasis and prolonged survival after single-agent use in xenograft models, and after combination with cabozantinib in RCC patient-derived xenograft models, the conduct of this trial is considered justifiable using the dose(s) and dosage regimen(s) of the investigational drug as specified in this clinical trial protocol. Refer to the M8891 Investigator's Brochure (IB) for further information about the nonclinical program. Based on the clinical data to date from the ongoing single agent study with M8891 (Part 1) and the known safety profile of cabozantinib, the safety measures such as stringent eligibility, routine safety monitoring along with AE reporting for the proposed study are considered adequate.

This clinical trial will be conducted in compliance with the clinical trial protocol, ICH GCP and any additional applicable regulatory requirements.

3.3.1

[figure not shown]
M8891

More detailed information about the anticipated benefits and risks based on nonclinical data of M8891 is presented in Section 3.1 and the M8891 IB.

CCI

CCI

Based on the currently available data, M8891 (parent drug) is predicted to exhibit a low drug-drug interaction (DDI) potential as perpetrator of CYP3A4 sensitive substrates at doses at the upper range of the estimated BED (60 mg QD). The DDI potential as victim of strong CYP3A4, 2C19 and 2C9 inhibitors is predicted to be weak, and as victim of a combined CYP3A4, 2C19 and 2C9 inhibitor to be only in the moderate range.

CCI

No relevant effects on cardiovascular, respiratory, or central nervous system function are anticipated from the in vitro and in vivo safety pharmacology studies for the expected clinically relevant exposures.

The lymphatic and hematopoietic system including the bone marrow, the spermatogenetic epithelium and epithelia of the gastrointestinal tract were the main toxicity target organs of M8891 in pivotal 4-week oral repeat-dose toxicity studies in rats and dogs with no observed adverse effect levels (NOAELs) of 3 mg/kg/day and 0.75 mg/kg/day, respectively. M8891 was devoid of genotoxic, phototoxic and skin irritating potential.

CCI

Since the start of Part 1, until the 16 Mar 2019 data cut, a total of 17 subjects with various solid tumors have received M8891 in doses ranging from 7 mg to 60 mg with a minimum of 3 subjects per dose level. Preliminary data from this ongoing Part 1 of the study have shown that the oral exposure of M8891 increased reasonably in direct proportion to the dose up to 35 mg QD, whereas at dose of 60 mg QD exposure seems to increase less than in direct proportion to the dose. No safety concerns have been raised (refer to M8891 IB). QT corrected for heart rate according to Fridericia (QTcF) interval prolongation is currently investigated in the ongoing Part 1 of the study using 12-lead triplicate digital ECGs. There is no preclinical or preliminary clinical evidence that M8891 is leading to QTcF interval prolongation.

3.3.2 Cabozantinib

Cabozantinib is indicated for the treatment of patients with mRCC. The recommended dosage of cabozantinib in mRCC is 60 mg once daily without food until the patient no longer experiences clinical benefit or experiences unacceptable toxicity ([Cabometyx USPI 2019](#)).

3.3.3 M8891 combined with cabozantinib

Promising signals for the activity of M8891 combined with cabozantinib have been observed in nonclinical studies (Refer to the M8891 IB).

Thromboembolic events have been reported with the use of cabozantinib or MetAP2 inhibitors and specific exclusion criteria have been defined to reduce the risk for this overlapping toxicity. More detailed information about the known and expected benefits and risks and reasonably expected AEs of M8891 and cabozantinib may be found in Sections 3.1 and 6.5.5, the M8891 IB, as well as the cabozantinib US-Prescribing Information (USPI).

Risks for potential DDIs of M8891 with cabozantinib are predicted to be small. This is based on mechanistic static modeling approaches using reported data for cabozantinib, i.e. an observed AUC increase of 38% when combined with the strong CYP3A4 inhibitor ketoconazole and a total fraction metabolized of 0.7 (worst case scenario considering 27.3% renal elimination), respectively ([Nguyen 2015; Lacy 2015](#)). Combining with nonclinical DDI and human exposure data of M8891 (Refer to the M8891 IB) a small AUC ratio of only 1.2 (maximal 1.2-fold increase in cabozantinib

exposure) based on time dependent inhibition (TDI) of CYP3A4 by M8891 was estimated. Because labeling information recommends a dose adaption of cabozantinib when used in combination with strong inducers or inhibitors of CYP3A4 only, it is sufficient to monitor cabozantinib exposure when combined with M8891. Based on information reported for cabozantinib, the victim potential of M8891 - when combined with cabozantinib - is considered as very low.

Overall, the available clinical data generated to date indicate a positive benefit risk profile for this new combination and therefore it is considered justifiable to conduct the study, as specified in this protocol.

4 Trial Objectives

